No unpublished information contained herein may be disclosed without the prior written approval of Verona Pharma plc.

CONTACT LIST

Investigator: Study Location:	[name] Medicines Evaluation Unit Ltd [name] United Kingdom [name]
Sponsor	Verona Pharma plc [name] United Kingdom [name]
Sponsor's Medical Monitor:	[name] [contact] [contact]
Email address for reporting SAEs:	[contact]
Central Laboratory (Pharmacokinetics)	LGC [name] United Kingdom [contact]
Local Laboratory (Safety Laboratory Tests)	The Doctors Laboratory [name] United Kingdom
Central Review of ECGs and Holter Monitoring	ERT [name]

DETAIL OF AMENDMENTS SINCE THE PREVIOUS VERSION

Section 4.2: Exclusion Criterion no. 6 has been amended to remove the prohibition against prior exposure to RPL554.

SYNOPSIS

Title of Study:	A Phase II, randomised, double blind, placebo controlled, three way crossover study to assess the bronchodilator effect of RPL554 administered in addition to open label tiotropium in patients with COPD.		
Protocol Number:	RPL554-CO-202		
EudraCT Number:	2016-004450-15		
Phase:	II		
Sponsor:	Verona Pharma plc		
Principal Investigator:	[name]		
Study Centre(s):	Medicines Evaluation Unit Ltd [name] United Kingdom (UK)		
Planned Study Period:	Estimated: January to April 2017		
Objectives:	Primary Objective To investigate the bronchodilator effect on peak forced expired volume in 1 second (FEV ₁) (measured in first 4 hours after dosing) and average (measured as the area under the curve [AUC]) FEV ₁ over 12 hours of nebulised RPL554 dosed twice daily for 3 days (five total doses), as compared to placebo, when administered in addition to once daily tiotropium.		
	Secondary Objectives		
	• To investigate the effect of twice daily nebulised doses of RPL554, as compared to placebo, when administered in addition to tiotropium on lung volumes		
	• To assess the bronchodilator effect on peak FEV ₁ (measured in the first 4 hours after dosing) and average (measured as the area under the curve [AUC]) FEV ₁ over 12 hours of nebulised RPL554 after the first dose as compared to placebo, when administered in addition to tiotropium		
	• To analyse plasma concentrations and assess the steady state pharmacokinetics of RPL554 when administered in addition to tiotropium		
	• To assess the tolerability and safety of twice daily nebulised doses of RPL554 in addition to tiotropium		
	• To assess the dose response of two different doses of RPL554 on peak, average (0 to 12 hours), and morning trough FEV ₁ on Day 3 when dosed in addition to tiotropium		
	• To determine the onset of action of RPL554 when administered with tiotropium (after the first dose)		
	• To investigate the bronchodilator effect of nebulised RPL554, or placebo, administered in addition to tiotropium on average FEV ₁ over 4 hours after each morning dose		
	• To investigate the effects of RPL554 on specific airway conductance (sGaw) and lung volumes (residual volume [RV], functional residual capacity [FRC]) when administered in addition to tiotropium.		
	Exploratory Objectives		
	• To examine the effect of RPL554 on top of tiotropium on average FEV ₁ over 24 hours after 3 days of dosing		
	• To assess morning trough FEV ₁ prior to the final dose of study treatment		

Study Design and Methodology:	This is a Phase II, randomised, double blind, placebo controlled, complete block three way crossover study to investigate combination treatment with nebulised RPL554 and tiotropium dry powder inhaler (DPI) in patients with moderate to severe chronic obstructive pulmonary disease (COPD). It is planned to randomise up to 30 patients to get 24 evaluable patients at one study centre. Patients will be screened for eligibility (Visit 1), including a reversibility test with salbutamol between 7 and 21 days before the first dose of study treatment. Eligible patients will then attend three separate 3 day treatment periods (Treatment Periods 1 to 3) each separated by a 7 to 21 day washout period (taken from last
	dose of study treatment).
Study Procedures:	During each treatment period, patients will be present at the study centre from the morning of Day 1 until the morning of Day 4, although they will be able to leave the facility at the discretion of the study centre personnel. Overnight residency is required on Day 3 of each treatment period. Patients will be randomised pre-dose on Day 1 of Treatment Period 1.
	During each treatment period, patients will be dosed with tiotropium once daily each morning (Day 1 to Day 3) and either RPL554 or placebo twice daily (in the morning and evening) on Day 1 and Day 2 and once in the morning only on Day 3 (total of 5 doses of RPL554 or placebo in each treatment period; there is no evening dose of RPL554 or placebo on Day 3 of each treatment period).
	The pre-dose FEV_1 at Day 1 of Treatment Period 2 and Day 1 of Treatment Period 3 must be within $\pm 20\%$ of the pre-dose FEV_1 at Day 1 of Treatment Period 1, in order to ensure consistent baseline FEV_1 for each study treatment.
	The following provides a brief overview of the major procedures to be performed during each treatment period.
	The following will be performed at Day 1 of each treatment period:
	• Measurements of lung function (FEV ₁ and forced vital capacity [FVC]) by spirometry pre-dose and up to 12 hours post-dose
	• 12-lead electrocardiogram (ECG) pre-dose and up to 4 hours post dose and vital sign (supine) measurements pre-dose and up to 12 hours post-dose
	• Measurement of lung volumes by whole body plethysmography pre-dose
	The following will be performed on Day 2 of each treatment period:
	• Measurement of lung function (FEV ₁ and FVC) by spirometry pre-dose and for up to 4 hours post-dose
	• 12-lead ECG pre-dose and up to 2 hours post dose and vital sign (supine) measurements pre-dose and up to 12 hours post-dose
	• Measurement of lung volumes by whole body plethysmography pre-dose and at 1.25 hours post-dose
	• Holter monitoring pre-dose and up to at least 24 hours post-dose.
	The following will be performed at Day 3 of each treatment period:
	• Measurements of lung function (FEV ₁ and FVC) by spirometry pre-dose and up to 24 hours post-dose
	• 12-lead ECG and vital signs (supine) measurements pre-dose and up to 24 hours post-dose
	• Pharmacokinetic blood sampling pre-dose and up to 24 hours post-dose
	• Laboratory safety tests (haematology and biochemistry) at 24 hours post-dose
	The 24-hour assessments and Holter removal will be performed prior to discharge from the study centre on Day 4.
	Adverse events will be recorded throughout the study.
Number of Patients Planned:	24 evaluable patients (randomise up to 30 patients)

Main Criteria for Eligibility:	Inclusion Criteria
	Male and female patients with moderate to severe COPD, with a post-bronchodilator FEV_1 of 40 to 80% of predicted. They must have a baseline increase in FEV_1 of ≥ 150 mL after use of four puffs of salbutamol. They must have at least a 10 pack-year smoking history, and may be an ex-smoker or current smoker.
	Exclusion Criteria
	Patients must be clinically stable without recent COPD exacerbations or hospitalisations. They must not have uncontrolled disease or chronic heart failure.
Study Treatments:	All study treatments will be administered using the inhaled route.
	Patients will receive the following three dose treatment combinations (DPI treatment plus nebulised treatment) in a randomised sequence during Treatment Periods 1 to 3:
	Tiotropium 18 μg once daily + RPL554 6 mg twice daily Tiotropium 18 μg once daily + Placebo twice daily Tiotropium 18 μg once daily + RPL554 1.5 mg twice daily
	Each morning during each 3 day period, the DPI treatment (tiotropium; Spiriva [®] HandiHaler [®]) will be administered first followed immediately (starting within 2 minutes) by the nebulised treatment (RPL554 or placebo). The nebulised treatment (RPL554 or placebo) only will be repeated in the evening on Day 1 and Day 2, 12 hours after the morning dose; there is no evening dose of study treatment on Day 3 of each treatment period.
	The DPI treatment will be administered open label and the nebulised treatment will be administered double blind.
	The nebulised treatment (RPL554 or placebo) will be administered using a standard Jet nebuliser (PARI LC SPRINT [®] plus a PARI TurboBOY [®] SX compressor unit).
	The RPL554 formulation is a sterile suspension supplied as sterile stock suspensions of micronised RPL554 in pH 7 phosphate buffered saline, containing surfactants to aid suspension. The placebo is the same as the RPL554 suspension except that the active RPL554 ingredient is omitted, i.e. it consists of pH 7 phosphate buffered saline and surfactants only. It is thus a clear solution rather than a pale yellow suspension; there is no known inert yellow solid that would be acceptable for inhalation, and therefore a visually matching placebo could not be developed.
Duration of Treatment:	The approximate planned duration for each patient will be up to 82 days: 7 to 21 day screening period, up to 9 days treatment (three treatment periods of 3 days each separated by a 7 to 21 day washout period, taken from last dose of study treatment) and an end of study visit 4 to 10 days after the last treatment visit (Day 4 of Treatment Period 3).
Statistical Methods:	Treatments will be compared using analysis of covariance adjusting for treatment, period, patient and baseline. Multiplicative models will be used for FEV_1 and outcome from whole body plethysmography and additive models for blood pressure, pulse rate and ECG heart rate. RPL554 treatments will first be compared to placebo using a closed test procedure starting with the highest dose of RPL554.
Sample Size:	This is a complete block three-way crossover study. Assuming a residual coefficient of variation of 6% for peak FEV_1 , 24 patients will give an 80% power to detect a pairwise difference in maximum FEV_1 of 5.1%.

TABLE OF CONTENTS AND LIST OF TABLES AND FIGURES

Table of Contents

SPON	NSOR	SIGNAT	URE PAGE	2
INVE	ESTIG	ATOR SI	GNATURE PAGE	3
CON	FIDE	NTIALIT	Y STATEMENT	3
CON	ТАСТ	LIST		4
DET	AIL O	F AMEN	DMENTS SINCE THE PREVIOUS VERSION	5
SYN	OPSIS	5		6
TAB	LE OF	FCONTE	NTS AND LIST OF TABLES AND FIGURES	9
	Table	e of Conter	nts	9
	List c	of Tables a	nd Figures	.12
LIST	OF A	BBREVL	ATIONS AND DEFINITION OF TERMS	.13
1	INTR	ODUCTI	ON	.15
	1.1	Disease a	nd Study Treatment Review	.15
	1.2	Summary	v of Risks and Benefits	.17
2	OBJE	ECTIVES.		.18
	2.1	Primary (Objective	.18
	2.2	Secondar	y Objectives	.18
	2.3	Explorate	bry Objectives	.18
3	INVE	ESTIGAT	IONAL PLAN	.19
	3.1	Overall S	tudy Design and Plan Description	.19
	3.2	Discussio	on of Study Design, including the Choice of Control Groups	.20
	3.3	Planned I	Duration of the Study	.20
	3.4	Definition	n of the End of the Study	.21
4	SELE	ECTION C	OF STUDY POPULATION	.21
	4.1	Inclusion	Criteria	.21
	4.2	Exclusion	n Criteria	.22
	4.3	Removal	of Patients from Therapy or Assessment	.23
		4.3.1	Study Treatment Discontinuation	.24
		4.3.2	Patient Withdrawal	.24
		4.3.3	Study Discontinuation	.24
		4.3.4	Replacement Policy	.24
5	STUI	OY TREA	TMENTS	.25
	5.1	Study Tre	eatments Administered	.25
	5.2	Identity o	of Study Treatments	.25
		5.2.1	RPL554 and Placebo	.25
		5.2.2	Tiotropium DPI	.26
	5.3	Preparatio	on and Labelling	.26
		5.3.1	Nebulised RPL554 and Placebo	.26
		5.3.2	Tiotropium DPI	.26

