1.2 Summary of Risks and Benefits

Data from non-clinical studies suggest a potential for hypotension and tachycardia. However, RPL554 has been administered to over 240 subjects in clinical studies to date and has been well tolerated in moderate-severe COPD patients, healthy subjects, asthmatics and allergic rhinitics. No SAEs have been reported with RPL554 to date. The most common adverse events that have been reported at least twice in subjects who have received single or multiple doses of the nebulised suspension of RPL554 were generally mild and in descending order of frequency are headache, cough, dizziness, and palpitations. Adverse events for single and multiple dose studies are summarised in Investigator's Brochure Section 6.3.

The suspension formulation of RPL554 is pH balanced, and has favourable non-clinical toxicology and pharmacokinetic data. There were no effects on embryo-foetal survival and development in the rat. In the rabbit there was an effect on implantation at the highest dose tested which could be related to a pharmacological effect of RPL554, however there was no effect on embryo-foetal survival and development.

There has been no evidence of significant adverse events related to the cardiovascular or gastrointestinal systems, except associated with an increase in heart rate at high doses (12 mg to 24 mg). These small increases in heart rate may relate to the PDE3 inhibitory activity of the compound. In single dose studies there appears to be an increase in the rate of headache, which is most pronounced at doses over 6 mg. There was no other apparent dose related adverse events, with the exception of palpitations in patients dosed at 24 mg. Results from multiple dose data in patients with COPD suggests a transient increase in dizziness, the majority of which occurred during spirometry or dosing; otherwise, the rate of adverse events was similar in RPL554 and placebo treated patients. There was an apparent increase in mild adverse events in healthy subjects treated with high doses of RPL554, which may be associated with the higher serum levels in healthy subjects than in those with obstructive lung disease.

As RPL554 is currently planned to be administered for only 3 days (five doses) in this study, any benefit to the patients will be restricted to the immediate short-term.

2 **OBJECTIVES**

2.1 **Primary Objective**

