10.4.7 Safety

Safety data including safety laboratory tests, 12-lead ECG and Holter parameters, vital signs and physical examinations, will be summarised by treatment group and time point of collection, when appropriate. For continuous variables, the change from baseline (pre-dose at each treatment visit) to each post-dose time point will also be calculated and summarised. Data will further be illustrated by shift tables (showing changes from low/normal/high) and shift plots for selected time points. Separate listings will be generated of abnormal values occurring after the first dose of study treatment.

Coded adverse event terms will be presented by system organ class (SOC) and preferred term and summarised by treatment group. A summary table by treatment group with total number and number of patients with adverse events, SAEs, adverse events leading to discontinuation of study treatment, causally related adverse events and severe adverse events will be produced. Further SAEs, causally related adverse events and adverse event of each intensity will be summarised by SOC and preferred term.

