6.18.3 Vital Signs

The AUC parameters will be calculated using the linear trapezoidal rule. The peak pulse rate will be computed as the maximum value in the 4 hours after dosing minus the pre-dose Day 1 baseline value.

Peak (measured in first 4 hours after dosing) and AUC_{0-4h} pulse rate will be derived.

Vital sign observed values and change from baseline by parameter (unit) will be summarised over time.

In addition, 'substantial' changes from baseline will be categorised as follows: change from baseline in systolic/diastolic blood pressure (BP) (systolic BP [>±40 mmHg], diastolic BP [>±20 mmHg]) and pulse rate [>±30 bpm]). The number

and percentage of patients with changes from baseline as categorised above will be summarised separately for positive and negative changes over time and at any postbaseline time point.

All vital sign data will be listed including change from baseline and flags for substantial changes from baseline.,

A listing of clinically significant vital signs recorded throughout the study will be provided.

Mean (±SEM) figures will be presented for changes from baseline blood pressure and pulse rate data for each treatment day. The three study treatments will be represented by different colours on the figures at each postdose timepoint.

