6.18.7 Safety Analyses

Peak (measured in first 4 hours after dosing) and AUC_{0-4h} pulse rate and heart rate will be analysed.

Peak and AUC_{0-4h} for the pulse rate and heart rate will be analysed by comparing between the three study treatments using ANCOVA models with fixed factors for

treatment, period and patient, and using the baseline measurement of the treatment day (pre-first dose in a treatment period) as a covariate. The combination of tiotropium + RPL554 will be compared to tiotropium alone for each of the two doses of RPL554. Results of the comparisons will be expressed as the least squared means with 95% confidence interval (CI) and associated, 2-sided p-value.

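### The synopsis lists blood pressure among the variables to be modelled, but the SAP's safety ANCOVA covers only pulse rate and heart rate and the omission is not declared

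*Protocol*

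**What the plan says.** **Protocol, Synopsis (Statistical Methods).** "Treatments will be compared using analysis of covariance adjusting for treatment, period, patient and baseline". The next sentence assigns multiplicative models to FEV1 and plethysmography, and "additive models for blood pressure, pulse rate and ECG heart rate".

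**Protocol 1.2.** "Data from non-clinical studies suggest a potential for hypotension and tachycardia". The text goes on to report good tolerability in over 240 subjects.

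**Protocol 10.3.2 and 10.4.7.** Section 10.3.2 lists blood pressure as a safety measurement but defines a peak and an AUC0-4h for pulse rate only. Section 10.4.7 says safety data, vital signs included, "will be summarised by treatment group and time point of collection, when appropriate". It names no model for any safety variable.

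**SAP 6.18.3.** "Vital sign observed values and change from baseline by parameter (unit) will be summarised over time". The section adds counts of substantial changes ("systolic BP [>±40 mmHg], diastolic BP [>±20 mmHg"), with rises and falls shown separately, and mean (±SEM) change plots with all three treatments.

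**SAP 6.18.7.** "Peak and AUC_{0-4h} for the pulse rate and heart rate will be analysed by comparing between the three study treatments", by ANCOVA with treatment, period and patient as fixed factors and the pre-first-dose value as covariate. Blood pressure is absent.

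**SAP 6.19.** The declared changes are the PK set definition, the form of the peak parameters, the dropped AUC0-24h, the added airway resistance endpoint and the rescue-medication derivation.

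**The concern.** The synopsis clause names three variables. Two reached the SAP's model and one did not, and the section meant for such changes is silent. Protocol 10.1 requires departures from the protocol analysis to be detailed and justified in the study report. An undeclared one may be overlooked at that stage.

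Protocol 3.2 justifies the crossover by inference from differences within patients. A table of mean changes by treatment does not use that pairing and gives no interval for the difference from placebo. After the trial, a reader could see whether mean blood pressure looked lower on RPL554, but could not say from the planned outputs how large a fall the data are compatible with. For the other cardiovascular effect named in the same sentence of protocol 1.2, tachycardia, the SAP gives that answer twice: once for pulse rate and once for ECG heart rate.

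**Working it through.** **1. Does any other SAP text supply the missing analysis?**

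| Place | Blood pressure modelled? | Pulse rate modelled? | ECG heart rate modelled? |
|---|---|---|---|
| Protocol synopsis | yes, additive | yes, additive | yes, additive |
| Protocol 10.3.2 | measured; no derived parameter | peak and AUC0-4h defined; no model | measured; no derived parameter |
| Protocol 10.4.7 | no model | no model | no model |
| SAP 6.18.3, 6.18.4 | descriptive only | peak and AUC0-4h derived | peak and AUC0-4h derived |
| SAP 6.18.7 | no | yes | yes |
| SAP 6.19 | not mentioned | – | – |

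The general ANCOVA sentence in SAP 6.12.1 does not fill the gap. It specifies multiplicative models with a log baseline, does not name blood pressure, and follows a paragraph in SAP 6.12 that sends safety and tolerability to a separate section.

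In the protocol body, ECG heart rate has the same standing as blood pressure: it is measured, with no derived parameter and no model. The SAP models it all the same. Within the protocol, only the synopsis clause supports that, so the SAP took up part of the clause and left blood pressure out.

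**2. The plan's own figure, to confirm the variance set-up.** Inputs from protocol 10.5: residual CV 6%, 24 patients, 80% power. Two-sided 5% is from protocol 10.4.

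- Log-scale SD: s = √ln(1 + 0.06²) = 0.0599.
- Standard error of a pairwise difference: s × √(2/24) = 0.0599 × 0.2887 = 0.0173.
- Residual df: 3 × 24 = 72 observations, less 1 (mean), 23 (patients), 2 (treatments), 2 (periods) and 1 (covariate) = 43.
- Detectable log difference at 80% power (noncentral t, 43 df): 0.0496, a ratio of 5.08%, against 5.1% stated. Power at 5.1% is 80.2%.
- 0.051 × 1.3 L = 66 mL, as stated.

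The sample-size statement reproduces. It does not bear on blood pressure, but it supports using the same structure below.

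**3. What the omitted comparison could deliver.** The documents give no within-patient SD for blood pressure, so the range below is an assumption.

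95% CI half-width = t(0.975, 43) × SD × √(2/24) = 2.017 × SD × 0.2887

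| Assumed SD (mmHg) | 95% CI half-width (mmHg) | Difference detectable at 80% power (mmHg) |
|---|---|---|
| 5 | 2.9 | 4.1 |
| 8 | 4.7 | 6.6 |
| 10 | 5.8 | 8.3 |
| 12 | 7.0 | 9.9 |

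The formula assumes complete data on 24 patients and ignores the small loss of precision from adjusting for a baseline that varies between periods.

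**4. Baseline.** SAP 6.2 prescribes time-matched Day 1 baselines for vital signs and ECG. SAP 6.18 describes change from the pre-dose value of each treatment day. SAP 6.18.7 uses the pre-first-dose value of the period. Post-dose readings on Day 1 are already on treatment, so the time-matched rule, read literally, would subtract from the Day 2 and Day 3 changes any fall already present on Day 1. A restored analysis has to say which baseline it uses.

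**The case against.** The strongest reply is that the SAP follows the protocol body. Modelling of blood pressure rests on one synopsis clause, protocol 10.4.7 is descriptive, and no blood pressure parameter, day or time window is defined anywhere. This stands in part: the inconsistency begins inside the protocol and must be settled there too. It does not clear the SAP, because the synopsis is current text, 10.4.7 names no model for pulse or heart rate either, and 6.19 declares other changes but not this one.

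A second reply is that modelling heart rate matches the clinical experience. Protocol 1.2 reports no evidence of significant cardiovascular adverse events apart from those associated with heart rate increases at high doses. That could justify leaving blood pressure descriptive, but the SAP does not give that reason.

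Three stronger readings are tempting, and the documents do not support them.

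- A reader might infer that hypotension gets no treatment information at all. SAP 6.18.3 plans changes by treatment, separate counts of falls and rises, and mean plots showing all three treatments.
- A reader might infer that a moderate mean fall would go unseen because the systolic flag acts only beyond 40 mmHg. The flag concerns single readings. Mean summaries and plots sit beside it, and the half-width of a mean contrast is not comparable with an individual threshold.
- A reader might take hypotension to be one of only two risks named. Protocol 1.2 also lists headache, cough, dizziness and palpitations, and the hypotension statement comes from non-clinical data.

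It is also fair that more contrasts bring more chance findings: two measures, two pressures and two doses make 8 per day, or 24 if all three days are used.

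**Conclusion.** The point holds as a discrepancy with a practical consequence. The synopsis specifies an additive ANCOVA for blood pressure, SAP 6.18.7 leaves it out, SAP 6.19 does not declare this, and the protocol body does not match its own synopsis. What is lost is narrow: a within-patient difference from placebo with a confidence interval, for a potential risk named from non-clinical data. Descriptive information by treatment remains.

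The text comparison rests on no assumption. The size does: half-widths of about 2.9 to 7.0 mmHg depend on an assumed SD of 5 to 12 mmHg and complete data on 24 patients. They show the precision available, not an error in any planned conclusion, and the documents state no blood pressure margin against which to judge them. No efficacy inference, primary or secondary, is affected. The change is worth making because it is almost free and restores a comparison the protocol states.

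**What to change.** In SAP 6.18.7, add systolic and diastolic blood pressure with the same additive ANCOVA (treatment, period, patient).

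- **Measures:** the minimum over 0-4 h and AUC0-4h/4. The protocol names no blood pressure parameter, so the SAP must define one. Protocol 7.4.3 already schedules readings pre-dose and at 30 minutes, 1, 2 and 4 h on Days 1, 2 and 3.
- **Day:** the same day or days as the pulse-rate analysis, written out, since SAP 6.18.7 does not state them.
- **Covariate:** the pre-first-dose value of each period, with a sentence saying that the time-matched Day 1 baseline of SAP 6.2 does not apply to this model.
- **Reporting:** each dose versus placebo with a 95% CI, labelled descriptive with no multiplicity claim, consistent with how SAP 6.15 treats secondary endpoints.

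Align the protocol synopsis and 10.4.7 so that both name the same modelled safety variables. If blood pressure was meant to stay descriptive, declare and justify that in SAP 6.19 and correct the synopsis.

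The cost is SAP wording and a few more model runs on readings already planned, with no new procedures. The downside is 8 additional unadjusted contrasts for each day analysed.
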